8.0 Data Management

The PHQ-9 and GAD-7 must be entered into RedCap within 48 hours of being administered. The Crisis Protocol form must be entered into RedCap at the time the form is completed with the participant. All other assessments must be completed within the designated study visit windows then data entered into RedCap by designated site staff or designated study therapist within 14 days from the date assessments are completed.

Informed consent document	EPIC
Protocol registration form	WISER/OnCore
Depressive Symptoms - PHQ-9 ^{25,26}	RedCap
Anxiety Symptoms - GAD-7 ²⁷	RedCap
Demographic Information	RedCap
Fear of Recurrence Inventory Severity Subscale ²⁸	RedCap
Cancer Diagnosis & Treatment Information	RedCap
Current Medication Use	RedCap
Adverse Event (AE) Form	WISER/OnCore
AE Ascertainment Form	RedCap
Client Satisfaction Item	RedCap
Weekly Intervention Feedback	RedCap
Post-Intervention Interview	Files on a Secure Server
Progress Notes/Session Information Form	RedCap
Participant Change Status Form	RedCap

Cultural and Linguistic Adaptation of a Telephone-Based Intervention to Treat Depression and Anxiety in Hispanic Cancer Survivors

Wake Forest Baptist Comprehensive Cancer Center
WFBCCC # 01220

9.0 Statistical Considerations

9.1 Analysis of Primary Objective

Objective 2.1.1 will provide data on feasibility, including participation, accrual, adherence, and retention rates. We will calculate 95% confidence intervals for each feasibility measure to determine the range of estimates consistent with our data. We will track the number approached for screening, number screened, number eligible, and the percent who agree to participate. For those not meeting eligibility criteria, reasons will be summarized. The proportion of participants and corresponding 95% CI for participants who participated in the intervention sessions and those who completed all assessments will be computed; we will also calculate the percent who complete the Week 13 visit to assess retention. We will use one-sample tests of binomial proportions to compare participation, adherence, and retention rates to the hypothesized values of 50%, 75%, and 75%, respectively.

Qualitative Analyses. Interview transcripts and field notes will be reviewed independently by two staff members of the Q-PRO Shared Resource who will provide an integrative summary/synthesis of the interviews (identification of key points, potential themes, areas needing further exploration). The qualitative and quantitative analyses will be evaluated in a mixed-methods framework for consistency and discrepancies to refine the intervention for future studies.

9.2 Analysis of Secondary Objective

8.2.1 Analysis of Exploratory Objectives

In exploratory analyses, we will summarize the variables of interest (anxiety, depressive symptoms) fear of recurrence, satisfaction, and the therapist-participant relationship) by visit using descriptive statistics. Because this is a small pilot study, this information will be used to estimate variability for future study planning purposes, but not to estimate effect size or to test hypotheses, and the analyses will be considered exploratory.

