6.2 Supportive Care Guidelines-Crisis Protocol

Anxiety is measured by the GAD-7 at baseline and weeks 7 and 13. Depression is measured by the PHQ-9 at baseline and at weeks 7 and 13. When the data from either of these two forms are filled out, the study staff will document the scores to ensure participants have not indicated a significant worsening in anxiety or depression scores (1 standard deviation increase [rounded to the nearest integer] on the GAD-7 (Change \geq 4)⁷⁵ or PHQ-9 (Change \geq 6)⁷³ from baseline]. If there has been a significant change, the Project Manager will initiate the Crisis Protocol and complete a Crisis Protocol Event Form. During the course of a regularly scheduled participant contact, it may become evident that there is a need for immediate evaluation (e.g., active suicidal ideation, active psychotic symptoms, disorientation). Staff will be instructed to follow the Crisis Protocol and complete the Crisis Protocol Event Form. In both cases, the participant may be referred for mental health care by their primary care physician or by an emergency department physician.

Study staff will follow the steps outlined in the Crisis Protocol and participants will receive information about safety precautions and procedures to follow in the event of a crisis (i.e., the participant becomes imminently suicidal). Because active suicidal ideation is an exclusion criterion for the study, we anticipate that the risk of participants becoming suicidal during the study will be minimal. Further, in our prior studies, no participants randomized into the study became imminently suicidal. All study staff (therapists, research staff) will receive training on the Crisis Protocol and coping with participant distress that may be experienced during the consent, assessment and treatment procedures. In addition, there will be regular study team meetings to discuss clinical issues. [name] will review the status and progress of participants with the study therapists on a regular (at least monthly) basis. All participants will be contacted at Week 7 and Week 13 to assess the primary outcomes and depressive

Cultural and Linguistic Adaptation of a Telephone-Based Intervention to Treat Depression and Anxiety in Hispanic Cancer Survivors

Wake Forest Baptist Comprehensive Cancer Center
WFBCCC # 01220

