- Important Medical Event (IME) that may not result in death, be life threatening, or require hospitalization may be considered serious when, based upon medical judgment, they may jeopardize the patient or subject and may require medical or surgical intervention to prevent one of the outcomes listed in this definition. (FDA, 21 CFR 312.32; ICH E2A and ICH E6).

Reporting Requirements for above Study Descriptions:

- All unexpected hospitalizations regardless of grade
- All Grade 5 toxicities (deaths-expected and unexpected)
- All unexpected Grade 4 toxicities
- All additional reporting requirements as outlined in the protocol

Selected Adverse Events

A select list of adverse events include suicide attempts, psychosis, worsening anxiety, worsening depression, and suicidal ideation, should be reported as an adverse event, regardless of whether they resulted in an ER visit or hospitalization.

Definition of Worsening Anxiety or Depression

An adverse event form should be completed for any participant who indicates a significant worsening in anxiety or depression scores (1 standard deviation increase (rounded to the nearest integer) on the GAD-7 (Change ≥ 4)⁷⁵ or PHQ-9 (Change ≥ 6)^{73,74,51} from baseline). If there is a need for immediate treatment (e.g., active suicidal ideation, active psychotic symptoms, disorientation, and active substance abuse) at any point in time, staff persons will notify the co-PIs. In both cases, the participant may be referred for psychiatric care.

Data and Safety Monitoring: As adverse event reports are collected, all adverse events will be identified and reported to the co-principal investigators. The co-principal investigators are responsible for the review of all adverse event reports and determining whether any changes in the study protocol or informed consent are required to insure subject safety and welfare.

Clinical Monitoring: The co-PIs will meet with the study staff weekly to provide supervision and review the clinical status of all participants. Study staff will also notify at least one supervisor immediately if a patient shows the need for urgent treatment (e.g., suicidal intent, active psychosis). This type of information will be communicated immediately, with consultation about an appropriate course of action.

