9.3 Sample Size Justification

An N=12 sample size is quite standard for qualitative analyses to achieve thematic saturation. With 12 people, we will be able to calculate two-sided 95% confidence intervals around proportions of interest within 28%. Power is not applicable for this study in the absence of hypothesis testing.

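### Section 9.2 summarises GAD-7 and PHQ-9 only by visit, so the within-person worsening defined in Sections 6.2 and 7.0, and the SD of change, have no place in the planned analysis

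*Combined protocol and SAP*

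**What the plan says.** **Definition and capture.** Sections 6.2 and 7.0 call a rise from baseline of at least 4 on the GAD-7 or at least 6 on the PHQ-9 a significant worsening, and describe it as a one-SD increase.

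- Section 7.0: "An adverse event form should be completed for any participant who indicates a significant worsening in anxiety or depression scores". It also puts worsening among the selected events: "A select list of adverse events include suicide attempts, psychosis, worsening anxiety, worsening depression, and suicidal ideation". Two of the five are worsening itself, so three others remain.
- Section 6.2: "If there has been a significant change, the Project Manager will initiate the Crisis Protocol and complete a Crisis Protocol Event Form".
- Section 7.0 has every participant asked about adverse events at Weeks 7 and 13, and gives the co-principal investigators the review of each report.

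**Analysis.** Section 9.1 opens with "Objective 2.1.1 will provide data on feasibility, including participation, accrual, adherence, and retention rates" and goes on to the qualitative synthesis. Section 9.2 (in the subsection numbered 8.2.1) covers anxiety, depressive symptoms, "fear of recurrence, satisfaction, and the therapist-participant relationship) by visit using descriptive statistics". It gives the purpose as estimating variability for planning later studies, and rules out effect-size estimation and testing. Sections 9.3 to 9.6 cover sample size, accrual, study length and the absence of an interim analysis. No part of Section 9 plans a within-person change, a count of participants who worsened, or an adverse-event summary.

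**The concern.** Worsening is a paired quantity: it compares one person's later score with that person's own baseline. A by-visit summary drops the pairing. Its baseline figures also include everyone, while its Week 13 figures include only those still assessed.

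Two things are at stake. First, the pilot's results could show falling average scores and say nothing about how many participants met the protocol's own definition of worsening. Entry requires high scores, so averages may fall through regression to the mean alone. Second, a later study that analyses change needs the SD of change or the correlation between visits. By-visit SDs supply neither, so the summaries only partly serve the purpose that Section 9.2 gives them.

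**Working it through.** **1. The plan's own precision figure.** Section 9.3 says "we will be able to calculate two-sided 95% confidence intervals around proportions of interest within 28" percent. The Wald half-width at p = 0.5 and n = 12 is 1.96 × √(0.5 × 0.5 / 12) = 0.283, so 28% is reproduced. The exact interval at 6/12 has a half-width of 0.289. This point disputes no stated figure.

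**2. Do by-visit summaries determine worsening?** Take 12 constructed PHQ-9 baseline scores, 8 to 19, and 12 constructed Week 13 scores, 5 to 16. The means are 13.5 and 10.5, and the SD is 3.606 (variance 13) at both visits, whoever holds which score. With participants listed in order of baseline score:

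| Week 13 scores in that order | Changes | Rise of 6 or more | Correlation | SD of change |
|---|---|---|---|---|
| 5, 6, 7, … 16 | −3 for all | 0 of 12 | 1.00 | 0 |
| 14, 5, 16, 6, 7, 8, 9, 10, 11, 12, 13, 15 | +6, −4, +6, −5 (eight people), −4 | 2 of 12 | 0.31 | 4.2 |
| 14, 15, 16, 8, 9, 10, 11, 12, 13, 5, 6, 7 | +6 (three), −3 (six), −12 (three) | 3 of 12 | −0.70 | 6.6 |

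Check of the second row: the changes sum to 12 − 4 − 40 − 4 = −36, mean −3. Their squares sum to 36 + 16 + 36 + 200 + 16 = 304, so the variance is (304 − 12 × 9)/11 = 17.8 and the SD is 4.2. In general the variance of change is 13 + 13 − 2r × 13 = 26(1 − r), and r does not appear in a by-visit table.

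The third row needs a negative correlation. Even the most favourable arrangement of the other nine scores gives only −0.13, so 3 of 12 is not realistic with these scores. The second row makes the same point at a positive correlation.

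**3. How often might worsening occur?** The documents give no expected change and no correlation, so this is assumption throughout. Assume normal scores, a threshold of 1 SD (the protocol's description) and a mean improvement of 0.5 SD. Then the chance per person per scale is p = 1 − Φ(1.5/√(2(1 − r))), and the chance of at least one case in 12 is 1 − (1 − p)^12.

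| r | p | At least one of 12 |
|---|---|---|
| 0.3 | 10.2% | 73% |
| 0.5 | 6.7% | 56% |
| 0.7 | 2.6% | 27% |

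These figures must not be combined with step 2, where the SD is 3.606 and a rise of 6 is 6/3.606 = 1.66 SD. With that SD and a mean change of −3, p = 1 − Φ(9/(3.606 × √(2(1 − r)))), and the chance of at least one case is about 19%, 7% and 1% at r = 0.3, 0.5 and 0.7.

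**4. What a reported count would show.** Exact 95% intervals: 0/12 gives 0 to 26.5% (upper limit 1 − 0.025^(1/12)); 1/12 gives 0.2 to 38.5%; 2/12 gives 2.1 to 48.4%. At the 75% retention used in Section 9.1, 0.75 × 12 = 9 are assessed at Week 13, and 0/9 gives an upper limit of 33.6%.

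**5. Which score is the baseline?** Section 6.2 says both scales are measured at baseline. Table 3 marks them at screening, not at Week 0, and Section 6.1 repeats them only when more than 30 days have passed since screening. A change score needs these passages reconciled.

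**The case against.** The strongest reply is that worsening is already dealt with. Section 7.0 requires each case to be reported as an adverse event, and has the co-principal investigators decide whether the protocol or consent must change. Section 6.2 has staff check every score for within-person worsening, and Appendix C requires all adverse events to be entered in WISER. All of this stands. A reader might infer that worsening goes unreported or is concealed; the documents do not support that. What is missing is a study-level summary. The DSMC triggers in Section 7.0 (unexpected grade 4, unplanned hospitalisation, death) do not fill that gap, because a score rise alone does not meet them.

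A second reply is that this is a pilot of 12 with feasibility, adaptation and descriptive objectives, none of them safety. Section 9.3 says "Power is not applicable for this study in the absence of hypothesis testing", and Section 9.2 disclaims effect sizes, so it would be wrong to say that the plan sets out to claim a mean improvement. Weekly feedback, the closing interviews and the mixed-methods comparison in Section 9.1 could also bring harm to light, so it is too strong to say that nothing else could reveal it. That is fair, but none of these gives a count, and the addition proposed here tests nothing. Section 9.1 already attaches 95% intervals to proportions at this sample size.

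A third reply is that the data are held and can be tabulated at any time. They can. The plan nevertheless commits no one to do so, and leaves open the denominator, the baseline and the handling of participants without follow-up scores.

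**Conclusion.** The point holds as a gap in the analysis plan. Worsening is defined, captured and reviewed case by case, but Section 9 does not summarise it, and by-visit statistics cannot recover it or the SD of change. This follows from the structure of the summaries and needs no assumption about the data: the same visit means and SDs fit 0 or 2 of 12 worsened, with an SD of change of 0 or 4.2.

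How often worsening would occur cannot be settled from the documents. The 56% chance of at least one case per scale (27% to 73% over correlations 0.7 to 0.3) rests on an assumed 0.5 SD improvement, normal scores and a 1 SD threshold; other assumptions give figures as low as 1%. A reader might take the constructed pairings or the 56% as forecasts. They are not.

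The change is worth making because it is cheap and serves the plan's stated purpose. The gap in the analysis does not remove the case-by-case safety handling in Sections 6.2 and 7.0.

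**What to change.** Add to Section 9.2:

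- **Paired change.** Within-person change from the screening/baseline score at Weeks 7 and 13, as individual values, mean and SD, among participants with both scores.
- **Worsening.** Number and percent meeting the existing Section 7.0 definition on the GAD-7, on the PHQ-9 and on either, at each visit and at any time, each with an exact 95% interval. The denominator is those assessed at that time; for any time, those with at least one post-baseline score. Show beside it how many of the 12 enrolled lack a score, so that they are not counted as free of worsening.
- **Events.** Counts of enrolled participants with each selected adverse event (worsening anxiety, worsening depression and the three others), each SAE and each Crisis Protocol event.
- **Baseline.** State which score is the baseline, and reconcile Section 6.2 with Section 6.1 and Table 3.

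No threshold or clinical action changes. The cost is a few lines of text and one table, with no new data, visits or staff. The downside is wide intervals: 0/12 still allows 26.5% and 0/9 allows 33.6%, so the table should be labelled as description and not as evidence of safety.

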9.3 Sample Size Justification

An N=12 sample size is quite standard for qualitative analyses to achieve thematic saturation. With 12 people, we will be able to calculate two-sided 95% confidence intervals around proportions of interest within 28%. Power is not applicable for this study in the absence of hypothesis testing.

9.4 Estimated Accrual Rate

We will enroll 12 participants over six months at a rate of 2 participants per month.

9.5 Estimated Study Length

The study will span one year in duration.

Appendix A – Eligibility Checklist

IRB Protocol No.	WFBCCC Protocol No.
Study Title: Cultural and Linguistic Adaptation of a Telephone-Based Intervention to Treat Depression and Anxiety in Hispanic Cancer Survivors	
Principal Investigators: [name] & [name]	

Inclusion Criteria (as outlined in study protocol)	Criteria is met	Criteria is NOT met	Source Used to Confirm * (Please document dates and lab results)
Age \geq 18 years;			
Self-identify as Hispanic ethnicity			
Score \geq 10 on the GAD-7 and/or \geq 8 on the PHQ-9;			
History of (1) treated (newly diagnosed or recurrent) solid tumor cancers (Stage I, II, or III); (2) any stage lymphoma (Hodgkin's or non-Hodgkin's); (3) acute leukemia in remission for more than a year; (4) chronic myelogenous leukemia with stable disease (chronic phase disease); or (5) chronic lymphocytic leukemia (CLL) not requiring treatment or a change in treatment for more than 6 months.			
6-60 months post-treatment (surgery, chemotherapy, and/or radiation therapy) for cancer (If only received active surveillance for prostate cancer or lymphoma with no other cancer treatment, participant is ineligible.) The timeframe applies to the most recent completion of treatment if a participant had a cancer recurrence. It is acceptable to be on hormonal/maintenance therapies.			
Must be able to speak, read, and understand Spanish or English			
Resides in North Carolina			
Exclusion Criteria (as outlined in study protocol)	Criteria NOT present	Criteria is present	Source Used to Confirm * (Please document dates and lab results)
Current psychotherapy [regular appointment(s) with a mental health provider within the last 30 days]			

**Cultural and Linguistic Adaptation of a Telephone-Based Intervention to Treat Depression and Anxiety
in Hispanic Cancer Survivors**

Wake Forest Baptist Comprehensive Cancer Center
WFBCCC # 01220

Self-reported active alcohol or substance abuse within the last 30 days			
Past history of prostate cancer or non-Hodgkin's lymphoma with only active surveillance (i.e., no surgery, chemotherapy, or radiation therapy)			
Progressive cancer			
Global cognitive impairment based on self-reported diagnosis of dementia.			
Self-reported psychotic symptoms in the last 30 days (Item in Screening Form: "Have you seen things that aren't really there or have you heard voices when no one else was around within the last 30 days?")			
Active suicidal ideation with plan and intent			
Any change in psychotropic medications within the last 30 days			
Hearing loss that would preclude participating in telephone sessions (determined by brief hearing assessment administered by research staff). Individuals who can compensate for hearing loss through the use of a hearing device or TDD phone, and through the use of such devices are able to communicate with the study therapist by telephone, will be included. If the therapist cannot communicate with the participant by telephone, the participant will be excluded.			
Failure/inability/unwillingness to provide names and contact information for two family members or friends to serve as emergency contacts during the course of the study			

This subject is eligible / ineligible for participation in this study.

OnCore Assigned PID: _____

Signature of research professional confirming eligibility: _____

Date: _____ / _____ / _____

**Cultural and Linguistic Adaptation of a Telephone-Based Intervention to Treat Depression and Anxiety
in Hispanic Cancer Survivors**

Wake Forest Baptist Comprehensive Cancer Center
WFBCCC # 01220

Appendix B – Protocol Registration Form

DEMOGRAPHICS

Patient: Last Name: _____ First Name: _____

MRN: _____ DOB (mm/dd/yy): ____ / ____ / ____

ZIPCODE: _____

SEX: Male Female

Ethnicity (choose one): Hispanic

Non-Hispanic

Primary Diagnosis: _____

Date of Diagnosis: ____ / ____ / ____

PROTOCOL INFORMATION

Date of Registration: _____ / _____ / _____

MD Name (last): _____

Date protocol treatment started: _____ / _____ / _____

Informed written consent: YES NO

(consent must be signed prior to registration)

Date Consent Signed: _____ / _____ / _____

PID # (to be assigned by OnCore): _____

Protocol Registrar can be contact by calling [contact] between 8:30 AM and 4:00 PM, Monday – Friday.

Complete the eligibility checklist in WISER and then give the completed Eligibility Checklist and Protocol Registration Form must be hand delivered, faxed or e-mailed to the registrar at [contact] or [contact], respectively.

Appendix C – STRC Reporting Requirements

Data and Safety Monitoring Committee (DSMC) Serious Adverse Event (SAE) Notification SOP	Date: 02/11/2021
-------------------------------------------------------------------------------------------------	-------------------------

Mandatory DSMC SAE Reporting Requirements in WISER

This document describes reporting requirements of adverse events from **WFBCCC Investigator Initiated interventional trials to the Data and Safety Monitoring Committee (DSMC)**. A trial is considered a **WFBCCC Investigator Initiated interventional trial** if the following criteria are met:

- 1) The Principal Investigator (PI) of the trial is a member of a department at the Wake Forest University Baptist Medical Center.
- 2) WFBCCC is considered as the primary contributor to the design, implementation and/or monitoring of the trial.
- 3) The trial is designated as “Interventional” using the Clinical Research Categories definitions provided by the NCI in the Data Table 4 documentation.
(<https://cancercenters.cancer.gov/GrantsFunding/DataGuide#dt4>)

There are two distinct types of WFBCCC Investigator Initiated interventional trials based on where patient enrollment occurs. These include:

- 1) Local WFBCCC Investigator Initiated interventional trials defined as trials where **all patients are enrolled from one of the WFBCCC sites**. These include the main outpatient Cancer Center clinics (located in Winston-Salem) as well as WFBCCC affiliate sites located in Bermuda Run (Davie Medical Center), Clemmons, Lexington, High Point, or Wilkesboro.
- 2) Multi-Center WFBCCC Investigator Initiated interventional trials defined as trials where patients are enrolled from other sites in addition to WFBCCC sites.

There are three types of trials that are included in this category:

- a. Trials sponsored by the NCI Community Oncology Research Program (NCORP) that are conducted at multiple sites where the PI is a member of a department at the Wake Forest University Baptist Medical Center.
- b. Trials sponsored by Industry that are conducted at multiple sites and the PI is a member of a department at the Wake Forest University Baptist Medical Center.
- c. Trials sponsored by WFBCCC that are conducted at multiple sites and the PI is a member of a department at the Wake Forest University Baptist Medical Center.

All Adverse Events (AEs) and Serious Adverse Events (SAEs) that occur on any patients enrolled on WFBCCC Investigator Initiated Interventional trials must be entered into the WISER system. The only exception to this requirement is for patients enrolled on NCORP trials at non- WFBCCC sites. AEs and SAEs for NCORP patients enrolled at WFBCCC sites must be entered into the WISER system. Once these AEs and SAEs are entered in WISER, certain actions must be taken regarding the reporting of specific Adverse Events to the DSMC.

Cultural and Linguistic Adaptation of a Telephone-Based Intervention to Treat Depression and Anxiety in Hispanic Cancer Survivors

Wake Forest Baptist Comprehensive Cancer Center
WFBCCC # 01220

All Adverse Events that occur during protocol intervention (defined below) and are coded as either 1) **unexpected grade 4**, 2) **unplanned inpatient hospitalization > 24 hours (regardless of grade)**, or **grade 5 (death)** must be reported to the DSMC using the SAE console in WISER.

A research nurse or clinical research coordinator when made aware that an adverse event meets one of the above criteria has occurred on a WFBCCC Investigator Initiated interventional trial, is responsible for informing a clinical member of the DSMC by phone (or in-person) about the adverse event. The nurse/coordinator should contact the treating physician prior to calling the DSMC clinical member to obtain all details of the SAE, as well as all associated toxicities to be recorded along with the SAE. In addition, this nurse or coordinator is responsible for entering the adverse event information into the SAE console in WISER. Once the adverse event has been entered into the SAE console an email informing the entire DSMC will be generated.

THESE REPORTING REQUIREMENTS APPLY TO any staff member on the study team for a WFBCCC Institutional Interventional trial. Ultimately, the protocol PI has the primary responsibility for AE identification, documentation, grading and assignment of attribution to the investigational agent/intervention. However, when an AE event as described above is observed, it is the responsibility of the person who observed the event to be sure that it is reported to the DSMC.

What is considered during protocol intervention?

During protocol intervention is considered to be the time period while a patient is on study treatment or during the time period within 30 days of last study treatment (even if patient begins a new (non-study) treatment during the 30 days). This window of 30 days should be the standard window to be used in all protocols unless a specific scientific rationale is presented to suggest that a shorter window can be used to identify events. If it is a trial sponsored by Industry and the sponsor requires a longer window for monitoring of SAEs, then the longer window of time specified by the sponsor should be followed.

What is considered as an Unexpected Grade 4 event?

Any grade 4 event that was not specifically listed as an expected adverse event in the protocol should be considered as unexpected. A grade 4 adverse event can be considered to be unexpected if it is an event that would not be expected based on the treatment being received or if it is unexpected based on the health of the patient. In either case, if there is any uncertainty about whether a grade 4 adverse event is expected or unexpected it should be reported to DSMC.

DSMC notification responsibilities of the person (e.g., nurse) handling the reporting/documenting of the SAE in WISER:

1. Make a phone call (or speak in person) to the appropriate clinical member of the DSMC according to the schedule as listed below (page if necessary).
2. Enter a new SAE into the SAE module that is located in the Subject>> CRA Console inWISER **WITHIN 24 HOURS** of first knowledge of the event. Information can be entered and saved, but the DSMC members will not be notified until a date is entered into the DSMC Notification Date Field. This will ensure that all persons that need to be made aware of the event (i.e., PI, study team members and DSMC members) will be notified; remember to file a copy of the confirmation.
3. Document that the appropriate person(s) on the DSMC has been contacted. Indicate the name of

the DSMC clinician that was contacted and the date and time contacted in the Event Narrative field in the SAE console of the particular subject.

4. Document whether or not the protocol should be suspended based on the discussion with the DSMC clinician. This is the major function of the email notification. Enter whether the protocol should be suspended in the Event Narrative Field.
5. Follow up/update the clinical member(s) of DSMC regarding any new developments or information obtained during the course of the SAE investigation and reporting process.

Elements needed to complete the SAE form in the Subject Console in WISER (see Screen Shot 3):

1. Event Date
2. Reported Date
3. Reported by
4. If Grade 5, enter Death Date
5. If Grade 5, enter Death occurred: within 30 days
6. Event Narrative: Brief description (include brief clinical history relevant to this event, including therapies believed related to event). Begin narrative with the DSMC clinician who was notified and Date/Time notified. In addition, state attribution by DSMC clinician as either “Unrelated”, “Unlikely”, “Possibly”, “Probably”, or “Definitely”. Always include the following here:
 - i. DSMC clinician name, date/time contacted and comments
 - ii. Date of last dose before the event
 - iii. Is suspension of the protocol needed? Y/N
7. Treating Physician comments
8. PI comments, if available
9. Protocol Attribution after discussion with DSMC clinician
10. Outcome (Fatal/Died, Intervention for AE Continues, Migrated AE, Not Recovered/Not Resolved, Recovered/Resolved with Sequelae, Recovered/Resolved without Sequelae, Recovering and Resolving)
11. Consent form Change Required? Y/N
12. SAE Classification ***This is required in order for the email notification to be sent***
13. Adverse Event Details – Enter all details for each AE associated with the SAE.
 - a. Course start date
 - b. Category
 - c. AE Detail
 - d. Comments
 - e. Grade/Severity
 - f. Unexpected Y/N
 - g. DLT Y/N
 - h. Attributions
 - i. Action
 - j. Therapy
 - k. Click ADD to attach the AE Detail to the SAE.
14. Enter Date Notified DSMC -- ***This is required for the email notification to be sent***
15. Click Submit. The auto-generated notification email will disseminate within 5 minutes. If you do not receive an email within 5 minutes, check that you have entered the “Date Notified DSMC” and

